at the start of the study and for up to 1 year after the study is completed, if there are changes that affect my financial disclosure status.

I agree to ensure that the confidential information contained in this document will not be used for any purpose other than the evaluation or conduct of the clinical investigation without the prior written consent of Amgen Inc.

Signature

Name of Principal <<or Coordinating>> Investigator Date (DD Month YYYY)

Title: An International, Randomized, Double-blind, Placebo-controlled, Phase 2 Study of AMG 479 with Exemestane or Fulvestrant in Postmenopausal Women with Hormone Receptor Positive Locally Advanced or Metastatic Breast Cancer

Study Phase: 2

Indication: Postmenopausal women with hormone receptor (HR)-positive, locally advanced or metastatic breast cancer who have disease progression during or within 12 months after completing prior adjuvant endocrine therapy or during the first prior endocrine therapy for metastatic disease

Primary Objective: To provide an estimate of the relative efficacy of Arm A (AMG 479 in combination with endocrine therapy [exemestane or fulvestrant] versus Arm B (AMG 479 placebo in combination with endocrine therapy [exemestane or fulvestrant]) as measured by the progression free survival (PFS) hazard ratio. This estimate will be precise enough to provide guidance for further development of AMG 479.for use in the planning of a phase 3 study in this patient population. Additionally, this study will provide qualitative estimates of PFS for treatment arms A and B.

Secondary Objectives: To investigate the effect of AMG 479 compared with placebo when administered in combination with exemestane or fulvestrant on:

- the safety and tolerability
- the impact to patient reported outcomes (PROs)
- the pharmacokinetics (PK) of AMG 479
- additional efficacy measures including clinical benefit rate, objective response rate, duration of response, time to progression (TTP), time-to-response, time-to-treatment failure, and survival time

Exploratory Objectives: To assess the potential effect of co-administration of AMG 479 and endocrine therapy (exemestane or fulvestrant) on the PK of the endocrine therapy (exemestane or fulvestrant).

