In order to safeguard the interest of the study subjects and maintain the study integrity, Amgen will form an unblinded data review team (DRT) that is external to the study team involved in the daily conduct of the study, but internal to Amgen to review safety data and efficacy analysis results.

Endpoints:

Primary: Progression free survival (PFS), as measured by Response Evaluation Criteria in Solid Tumors criteria (modified RECIST) per local review

Secondary:

- Clinical benefit (complete response, or partial response, or stable disease for ≥ 24 weeks as measured by modified RECIST per local review), objective response rate (complete and partial response as measured by modified RECIST per local review), duration of response, TTP, time-to-response, time-to-treatment failure, and survival
- Incidence of adverse events, abnormal laboratory values, and anti-AMG 479 antibody formation
- PK parameters of AMG 479
- Breast cancer related symptoms, health related quality of life, and skin toxicity burden

Exploratory: Objective response by tumor mutation status, biochemical concentrations and abundance of drug targets in tumor tissue and blood samples, genetic variations in drug metabolism genes and target genes (optional, separate informed consent required).

Sample Size: The study plans to randomize 150 subjects in a 2:1 ratio to Arm A: AMG 479 in combination with endocrine therapy (exemestane or fulvestrant) or Arm B: placebo in combination with endocrine therapy (exemestane or fulvestrant).

Key Subject Eligibility Criteria:

Inclusion

- Histologically or cytologically confirmed carcinoma of the breast with locally advanced or metastatic disease not amenable to surgery or radiation with curative intent (based on medical history review)
- Confirmation of HR (estrogen and/or progesterone receptor) positive disease using institutional standards for analysis of the primary tumor tissue or tissue obtained thereafter (based on medical history review)
- Amenable to receive endocrine therapy as per investigator discretion
- Disease progression while receiving prior endocrine therapy for locally advanced or metastatic breast cancer or recurrence while receiving prior endocrine therapy as adjuvant treatment or within 12 months of treatment discontinuation.
- Measurable or non-measurable disease, as defined by the modified RECIST criteria
- Eastern Cooperative Oncology Group performance status of 0 or 1

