Interim analyses of safety data will occur at the time 12 and 30 subjects have completed treatment administration for 2 months to assess safety and tolerability of the combination of AMG 479 or placebo with endocrine therapy (exemestane or fulvestrant). The DRT, will review cumulative safety data and make recommendations regarding study conduct. An interim analysis of efficacy and safety data is planned at the time 75 PFS events have occurred. This is estimated to occur approximately one month after the last subject is randomized. Summary statistics and Kaplan-Meier (K-M) plots of PFS by treatment arm, 80% confidence intervals for the estimated hazard ratio and the K-M estimated proportion of subjects without a PFS event at 6 months post-randomization will be generated. The stratified Cox model will be used to estimate the hazard ratio with respect to PFS (using the stratification factors) and to produce an 80% confidence interval for the hazard ratio.

All primary and secondary efficacy analyses will be conducted on the full analysis set. Subjects will be included in the analysis according to their randomized treatment assignment. The primary efficacy analysis will be performed when approximately 120 PFS events have been observed, where progression is based on local review. This is estimated to occur approximately 23 months after the first subject is randomized. At the time of the primary efficacy analysis, summaries will be provided for each safety, efficacy and PRO endpoint. The primary analysis of PFS will use the same methods utilized for the interim analysis of PFS.

Sponsor/Licensee: Amgen Inc.

Product: AMG 479 Protocol Number: 20060362 Date: Amendment 2, 01 June 2011

	Screen	study Treatment																	Safety FU°	Long-term FU ^p			
Cycle			1		2 2			3		4	5			6	7		8			Assess for			
Cycle		•			2		5		•	5			Ū		'		5		Roll Over ⁿ	ΗI			
Cycle Days	-28	1	2	15	1	15	1	15	1	15	1	15	1	15	1	15	1	15			DE/		
Study Week	-4		1	3	5	7	9	11	13	15	17	19	21	23	25	27	29	31	H		OR		
ENDOCRINE TREATMENT ADMINISTRATION ^a																			DE/		NO		
Exemestane		ł																\rightarrow	R	Х	ЗET		
Fulvestrant		Х		Х	Х		Х		Х		Х		Х		Х		Q4W		NO	Х	ISCF		
INVESTIGATIONAL PRODUCT ADMINISTRATIO	N																		RET		PID		
AMG 479 or Placebo		Х		Х	Х	Х	Х	Х	Х	Х	Х	Х	Х	Х	Х	Х	Х	Q2W	SC		۲Ľ,		
GENERAL AND SAFETY ASSESSMENTS																			PID		RAV		
Informed Consent	Х																		Å,		문		
Review of Eligibility	Х																		RA	х	.M.		

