- j Subjects with a positive bone scan at screening will continue to have bone scans performed every 11 to 12 weeks thereafter while on study treatment. Subjects with a negative bone Scans will not be required to continue this procedure. Confirmatory bone images at baseline (CT with bone windows or MRI) at baseline and on during study treatment are required for positive areas on baseline bone scan as specified in Section 7.1.1.
- k Subjects with a tumor marker CA 15-3 or CA 27-29 out of normal ranges at screening will continue to have this analyte analyzed while on study. The tumor marker selected at screening should remain the same throughout the study. Subjects with a tumor marker CA 15-3 or CA 27-29 within normal ranges at screening will not be required to continue this procedure.
- Tumor Sample (archived block, slides or fresh tissue collected for clinical care purposes) are to be obtained. A paraffin tumor block or fresh tissue from the most recent tumor tissue is preferred.
- m PRO questionnaires should be completed before any other study procedures and before the patient is informed of their disease status
- n Subjects will have a roll over visit, before initiating open-label AMG 479. This visit will allow assessment of roll over eligibility and will serve as the new baseline from which all changes will be compared. All subsequent visits and assessments will be performed according to the regular schedule of assessments continuing with the next per protocol visit after the last completed visit that occurred during blinded treatment.
- o Safety FU- Safety follow-up visit is to be completed 30 to 37 days after last administration of protocol treatment
- p All subjects who are alive at the time of discontinuation of protocol therapy will be followed approximately every 3 months for up to 48 months from the date of the last subject enrolled into the study to evaluate overall survival and disease status.

Page 95 of 113

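### Does analysing objective response rate on the full analysis set, when non-measurable disease is eligible, undermine that endpoint?

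*Combined protocol and SAP*

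**What the plan says.** Three statements in the synopsis bear on this point.

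- **Eligibility (Key Subject Eligibility Criteria, Inclusion):** "Measurable or non-measurable disease, as defined by the modified RECIST criteria". The synopsis sets no minimum or cap for either type.
- **Endpoint (Endpoints, Secondary):** "objective response rate (complete and partial response as measured by modified RECIST per local review").
- **Analysis set (Statistical Considerations):** "All primary and secondary efficacy analyses will be conducted on the full analysis set", followed by "Subjects will be included in the analysis according to their randomized treatment assignment".

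The same section promises that at the primary analysis "summaries will be provided for each safety, efficacy and PRO endpoint". The Secondary Objectives place ORR among "additional efficacy measures including clinical benefit rate, objective response rate, duration of response" and others. The Primary Objective concerns the PFS hazard ratio and says of it: "This estimate will be precise enough to provide guidance for further development".

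The synopsis does not mention an ORR restricted to measurable disease or a tabulation of measurable disease by arm. It also does not define the full analysis set, list the stratification factors or reproduce the modified RECIST response rules.

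**The concern.** Partial response is usually judged by shrinkage of measured lesions. If a subject has none, she may be unable to count as a partial responder, yet she stays in the ORR denominator. The full-set rate then combines two things: how often assessable tumours respond, and how many subjects had assessable tumours.

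At stake would be the reading of a low ORR, and its transfer to a later population with a different share of measurable disease. A chance imbalance in that share between arms would also move the observed difference. In a trial meant to inform later development, it is reasonable to ask whether the choice of denominator spoils the endpoint.

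**Working it through.** **Inputs from the documents.** 150 subjects randomized 2:1, that is 150 × 2/3 = 100 and 150 × 1/3 = 50, matching the arm sizes in Statistical Considerations. The plan states no response rate and no share of non-measurable disease, so it has no ORR figure to reproduce.

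**Assumed inputs.** Response in measurable disease 20% versus 10%. Non-measurable share *q* from 10% to 40%. Response rate *c* in non-measurable disease, equal in both arms, from 0 to 10%. The 80% interval level is borrowed from the plan's PFS analysis.

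**Step 1: size of the dilution.** Full-set ORR = (1 − q) × ORR in measurable disease + q × c. With c = 0 the rate is multiplied by (1 − q), so it falls by the fraction q.

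| q | Full-set ORR | Difference (points) | Ratio |
|---|---|---|---|
| 10% | 18% vs 9% | 9 | 2.00 |
| 20% | 16% vs 8% | 8 | 2.00 |
| 30% | 14% vs 7% | 7 | 2.00 |
| 40% | 12% vs 6% | 6 | 2.00 |

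At q = 30% with c > 0, the difference stays at 7 points and the ratio moves to 14.6/7.6 = 1.92 (c = 2%), 15.5/8.5 = 1.82 (c = 5%) and 17/10 = 1.70 (c = 10%).

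**Step 2: is the comparison biased?** Measurability is fixed before randomization, so q has the same expectation in both arms. If treatment has no effect on response, the expected full-set difference is zero for every q and c. Chance imbalance remains: at q = 30%, SE(qA − qB) = √[0.3 × 0.7 × (1/100 + 1/50)] = 7.9 points. A one-SE imbalance gives:

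- qA/qB = 32.6%/24.7%: 13.5% vs 7.5%, difference 5.9 points (from unrounded values).
- qA/qB = 27.4%/35.3%: 14.5% vs 6.5%, difference 8.1 points (from unrounded values).

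Both lie within about 1.1 points of the expected 7.0. The sampling SE of the difference itself is 5.0 points (Step 3). This is ordinary random variation, not bias.

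**Step 3: does the full set lose information?** At q = 30%, c = 0:

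- Full set: SE = √(0.14 × 0.86/100 + 0.07 × 0.93/50) = 5.01 points. The 80% half-width is 1.2816 × 5.01 = 6.4 points, and difference/SE = 7/5.01 = 1.40.
- Measurable subset (70 vs 35): SE = √(0.20 × 0.80/70 + 0.10 × 0.90/35) = 6.97 points. The half-width is 8.9 points, and difference/SE = 10/6.97 = 1.43.

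The subset has the larger difference and the wider interval, and the two nearly cancel. In a two-proportion test at two-sided 20% (pooled null variance, both tails counted), power is 0.492 on the full set and 0.509 in the subset. With c = 5% it is 0.466 against 0.509.

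**Step 4: does a decision depend on it?** The sample-size reasoning uses medians of 4, 5.5 and 6 months: 4/6 = 0.667 and 4/5.5 = 0.727, both as stated. These are PFS hazard ratios. No decision rule in the available text refers to ORR.

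**The case for a change.** The strongest case for the concern is about interpretation. Statistical Considerations says the trial should produce treatment-effect estimates that may help design a phase 3 program. An ORR level or absolute difference cannot be carried to a population with another case mix unless the share of measurable disease is known. Duration of response and time-to-response also concern responders, so knowing who could respond helps in reading them. Naming the subset before unblinding would avoid a later choice of denominator, and the cost would be one sentence and two table lines.

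The observation about transfer to another population is correct. It does not make the planned analysis wrong, for three reasons.

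- The full-set ORR estimates a well-defined quantity, the proportion of all randomized subjects who respond, and the comparison between arms is protected by randomization. A measurable-disease rate would stand beside it, not replace it.
- The absence cannot be established. The available text is a synopsis and an assessment schedule, and the schedule itself points to the body of the protocol: confirmatory bone images "are required for positive areas on baseline bone scan as specified in Section 7.1.1". A synopsis is not where one expects a supplementary subset or a baseline table to be specified. The share of measurable disease by arm is in any case observed only after enrolment.
- The mechanism is assumed. Whether subjects with only non-measurable disease can be scored as responders depends on the modified RECIST rules, which are not in the available text.

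The plan also lists clinical benefit, which counts stable disease lasting at least 24 weeks, so antitumour activity is not judged on complete and partial response alone.

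**Conclusion.** The concern does not hold. Following the plan as written gives a valid, unbiased comparison of response between the randomized arms. At an assumed 30% share of non-measurable disease with no responses there, the absolute difference shrinks from 10 to 7 points, while the rate ratio and the difference-to-SE ratio (1.40 against 1.43) are essentially unaffected. If non-measurable disease responds at an equal 5% in both arms, the ratio is 1.82 and power is about 4 points below that of the subset. That is little for a secondary endpoint on which no stated decision depends.

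These figures rest on assumed response rates, an assumed share and an assumed scoring rule; none is in the documents. The absence of bias does not depend on them, because it follows from randomization and analysis by assigned arm. A rate in measurable disease would be a reasonable optional table, but its absence from a synopsis is not a defect in the plan.

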Appendix A. Schedule of Assessments

- a Endocrine therapy (exemestane or fulvestrant) will be prescribed based on investigator discretion. Patients prescribed exemestane will have compliance reviewed and discussed with subject if needed at every clinic visit.
- b Clinical evaluation, including physical exam performed, and ECOG status
- c Height will only be collected at screening. Weight will be required pre-infusion to access the IVRS to obtain box assignment, quantity of vials and the volume of AMG 479 or placebo for infusion.
- d Vitals, include blood pressure and respiration rate, pulse, and temperature.
- e Blood chemistry will be analyzed at the local laboratory and will include: sodium, potassium, chloride, creatinine, CO₂, BUN, AST, ALT, alkaline phosphatase, and total bilirubin. Additionally fasting/non-fasting glucose will be assessed (fasting: screening, day 1 of cycles 1-4 then every second cycle, roll over treatment assessment [if applicable], and safety follow-up; non-fasting: day 15 of cycles 1-4, and day 1 cycle 5, then every second cycle)
- f Either serum creatinine or calculated creatinine clearance (by Crockcroft-Gault formula)
- g These laboratory assessments do not need to be performed on cycle 1 day 1 if they were performed during screening within 7 days of initiation of treatment
- h Blood collections for PK analysis will occur for AMG 479 (pre- and post-AMG 479 infusion thru cycle 3), for exemestane (only for subjects prescribed exemestane; pre- and post-exemestane administration thru cycle 3), and for fulvestrant (only for subjects prescribed fulvestrant; pre-fulvestrant IM injection only thru cycle 3). No PK sample collection is needed for post-fulvestrant IM injection. Thereafter, blood collection for PK analysis of AMG 479, exemestane, and fulvestrant will only occur pre-dose every 2 cycles, starting cycle 5.
- i Radiological assessments of the chest, abdomen and pelvis may occur by CT or MRI. The same technique used in screening must be used throughout the study. CT or MRI radiological assessments should occur on day 1 of cycle 3, then every 7 to 8 weeks thereafter.
- j Subjects with a positive bone scan at screening will continue to have bone scans performed every 11 to 12 weeks thereafter while on study treatment. Subjects with a negative bone Scans will not be required to continue this procedure. Confirmatory bone images at baseline (CT with bone windows or MRI) at baseline and on during study treatment are required for positive areas on baseline bone scan as specified in Section 7.1.1.
- k Subjects with a tumor marker CA 15-3 or CA 27-29 out of normal ranges at screening will continue to have this analyte analyzed while on study. The tumor marker selected at screening should remain the same throughout the study. Subjects with a tumor marker CA 15-3 or CA 27-29 within normal ranges at screening will not be required to continue this procedure.
- Tumor Sample (archived block, slides or fresh tissue collected for clinical care purposes) are to be obtained. A paraffin tumor block or fresh tissue from the most recent tumor tissue is preferred.
- m PRO questionnaires should be completed before any other study procedures and before the patient is informed of their disease status
- n Subjects will have a roll over visit, before initiating open-label AMG 479. This visit will allow assessment of roll over eligibility and will serve as the new baseline from which all changes will be compared. All subsequent visits and assessments will be performed according to the regular schedule of assessments continuing with the next per protocol visit after the last completed visit that occurred during blinded treatment.
- o Safety FU- Safety follow-up visit is to be completed 30 to 37 days after last administration of protocol treatment
- p All subjects who are alive at the time of discontinuation of protocol therapy will be followed approximately every 3 months for up to 48 months from the date of the last subject enrolled into the study to evaluate overall survival and disease status.

Page 95 of 113

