To investigate the effect of AMG 479 compared with placebo when administered in combination with exemestane or fulvestrant on biomarkers using biochemical analysis of blood and tumor samples, including the correlation between biomarker measurements at baseline and/or in response to treatment outcomes.

To investigate the effect of genetic variation in drug metabolism genes, breast cancer genes, and drug target genes on treatment outcomes (this part of the study is optional for subjects).

Hypothesis: This study will provide an estimate of the relative efficacy of AMG 479 in combination with endocrine therapy (exemestane or fulvestrant) versus AMG 479 placebo in combination with endocrine therapy (exemestane or fulvestrant) as measured by the PFS hazard ratio. Additionally, this study will provide the estimate of PFS for each treatment arm.

Study Design: This is a randomized, double-blind, placebo-controlled, phase 2 study. Subjects will include postmenopausal women with confirmed hormone receptor (HR)-positive, locally advanced or metastatic breast cancer, who have disease progression during or within 12 months after completing prior adjuvant endocrine therapy or during the first prior endocrine therapy for metastatic disease.

Based on investigator discretion, subjects will be prescribed an endocrine therapy of either exemestane or fulvestrant to be administered throughout the study. The study plans to randomize 150 subjects in a 2:1 ratio to Arm A: AMG 479 in combination with endocrine therapy (exemestane or fulvestrant) or Arm B: placebo in combination with endocrine therapy (exemestane or fulvestrant).

At least 45 of the 150 subjects randomized will be required to be prescribed to each endocrine therapy (exemestane and fulvestrant).

Study treatment with AMG 479 or placebo and endocrine therapy (exemestane or fulvestrant) will continue until disease progression, unacceptable toxicity, consent withdrawal, investigator discretion, initiation of a new anticancer treatment, or death.

Subjects randomized to placebo in combination with endocrine therapy (Arm B) may have the opportunity to continue receiving study treatment as open-label AMG 479 in combination with the endocrine therapy originally prescribed ('roll over treatment') upon disease progression.

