Study Treatment Dosage and Administration: The AMG 479 dose to be used in the study is 12 mg/kg IV every 2 weeks. Based on investigator discretion, subjects will be prescribed an endocrine therapy of either exemestane (25 mg tablets once a day [QD] by mouth [PO]) or fulvestrant (loading dose [500 mg intramuscular (IM) on study day 1, then 250 mg IM on study day 15] then 250 mg IM on study day 29 and every 28 days thereafter) to be administered throughout the study. **AMG 479 or placebo will be administered by IV infusion through a peripheral line or indwelling catheter using a nonpyrogenic, low protein binding filter with a 0.2- or 0.22-micron pore size in-line filter infusion set-up.**

Procedures: Informed consent, radiological assessments including bone scan and CT or MRI scans, clinical evaluations, hematology, coagulation factors, chemistry, HgbA1c, urine analysis, AMG 479, PK, biomarker and tumor tissue collection, concomitant medication collection, adverse event collection, and completion of PRO questionnaires.

Statistical Considerations: The sample size of 150 subjects randomized in a 2:1 ratio for test versus control (Test: AMG 479 + fulvestrant or exemestane; Control: placebo + fulvestrant or exemestane) is intended to generate treatment effect estimates that may aid in the design of a potential phase 3 program for AMG 479. The desired increase in the median PFS, for subjects that received AMG 479 in combination with endocrine therapy that is believed to be clinically meaningful is 2 months (with a minimum increase of 1.5 months). Using a median PFS of 4 months for the treatment of placebo in combination with endocrine therapy (exemestane or fulvestrant), a 2 month absolute increase (50% relative increase) in the median PFS translates into a hazard ratio of 0.667 [test(n = 100)/control(n = 50)] and a 1.5 month absolute increase (37.5% relative increase) in the median PFS translates into a hazard ratio of 0.727.

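### Appendix A times CT/MRI by both treatment cycle and study week without saying which governs, so unequal early dosing delays could slightly bias the PFS hazard ratio

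*Combined protocol and SAP*

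**What the plan says.** The primary endpoint (Synopsis, Endpoints) is "Progression free survival (PFS), as measured by Response Evaluation Criteria in Solid Tumors criteria (modified RECIST) per local review". Its hazard ratio is meant to inform phase 3 planning.

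Three statements set the timing of the assessments behind it:

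- Appendix A, footnote i: "CT or MRI radiological assessments should occur on day 1 of cycle 3, then every 7 to 8 weeks thereafter". The first on-study scan hangs on a treatment visit, and later scans are counted in weeks from it.
- The Appendix A grid has a study-week row as well as a cycle row. Cycle 3 day 1 stands under study week 9 and cycle 5 day 1 under week 17, and CT/MRI is every 8 weeks after that.
- Synopsis, Statistical Considerations: "the K-M estimated proportion of subjects without a PFS event at 6 months post-randomization will be generated". This clock starts at randomization.

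Bone scans have a similar pair of clocks. The grid marks one at cycle 4 day 1, while footnote j asks, for subjects positive at screening, for "bone scans performed every 11 to 12 weeks thereafter while on study treatment".

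On masking and dosing, the Synopsis says "This is a randomized, double-blind, placebo-controlled, phase 2 study" and "The AMG 479 dose to be used in the study is 12 mg/kg IV every 2 weeks".

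**The concern.** Cycle day and calendar week agree only while cycles run on time. A site that starts cycle 3 two weeks late and scans on that day has followed footnote i exactly, although the grid would have had the scan two weeks sooner. Later CT/MRI dates are counted from that scan, so the whole series stays shifted.

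Progression is dated when a scan shows it. If one arm has more early delays, its scans sit later on average and its recorded PFS changes without any change in the disease. AMG 479 is the only treatment that differs between the arms, so more toxicity-related delays in Arm A are plausible, though the documents give no rates. Blinding discourages deliberate timing of scans but does not prevent delays that toxicity causes. Any such bias is systematic, so more events would not shrink it.

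**Working it through.** **1. The plan's own figures.** From "Using a median PFS of 4 months for the treatment of placebo in combination with endocrine therapy" and a gain of 2 or 1.5 months, under exponential PFS the hazard ratio is the control median divided by the test median: 4/6 = 0.667 and 4/5.5 = 0.727. The first agrees with "translates into a hazard ratio of 0.667", and the second with the plan's figure for the minimum effect.

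**2. Precision, for scale.** With 120 events and 2:1 allocation, SE(log HR) = 1/√(120 × 2/3 × 1/3) = 1/√26.67 = 0.194. The 80% limits multiply and divide by exp(1.2816 × 0.194) = 1.28. Around 0.727 this gives 0.57 to 0.93, and around 0.667 it gives 0.52 to 0.85.

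**3. What a delay does under footnote i.** Cycle 3 day 1 is two 28-day cycles, or 8 weeks, after cycle 1 day 1; that is the start of study week 9. If it slips by d weeks, scans fall at 8+d, 16+d, 24+d and so on. A delay after the first scan changes nothing, because the footnote then counts weeks.

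**4. Effect on the hazard ratio.** Exponential PFS was simulated as seen only at scans, with a 4-month control median, 2:1 allocation and a Cox model with Efron ties. Only Arm A is delayed. The delay rates and lengths are assumptions. The ranges cover runs with 8-week spacing (±3 days) and runs with 7 to 8 week spacing, an assumed 16-month accrual and a 23-month cut-off.

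| Arm A delayed | Delay | True HR 1 | True HR 0.727 |
|---|---|---|---|
| none | – | 0.994 to 1.001 | 0.724 to 0.729 |
| 20% | 1 week | 0.974 | 0.712 |
| 20% | 2 weeks | 0.974 to 0.981 | 0.711 to 0.716 |
| 30% | 2 weeks | 0.964 to 0.971 | 0.704 to 0.709 |
| 50% | 2 weeks | 0.946 to 0.947 | 0.692 to 0.693 |
| 20% | 4 weeks | 0.985 to 0.992 | 0.718 to 0.724 |

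With scans fixed to the calendar, the 8-week runs give 1.001 and 0.729 whatever the delays.

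A longer delay does not mean more bias. With a 2-week delay, progression in weeks 0 to 8 is recorded at week 10 instead of 8, which is 2 weeks later. Progression in weeks 8 to 10 is recorded at week 10 instead of 16, which is 6 weeks sooner. Summing scan time × [S(previous scan) − S(scan)] over all scans, the mean recorded time for a delayed subject rises by only 0.37 weeks at the 4-month median.

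**5. Effect on the 6-month proportion.** Six months is 26.1 weeks, and 4 months is 17.39 weeks. A subject counts as event-free if free of progression at the last scan before the landmark, so the recorded chance is 0.5^(last scan/17.39).

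| Delay (weeks) | Last scan by 26.1 weeks | Recorded 6-month PFS | Change |
|---|---|---|---|
| 0 | 24 | 0.384 | – |
| 1 | 25 | 0.369 | −0.015 |
| 2 | 26 | 0.355 | −0.029 |
| 3 | 19 | 0.469 | +0.085 |
| 4 | 20 | 0.451 | +0.067 |

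These are changes per delayed subject. If 20% of an arm is delayed, the arm's estimate moves by 0.2 × 0.085 = +1.7 points for a 3-week delay, and by 0.2 × (−0.029) = −0.6 points for a 2-week delay.

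**The case against.** The strongest reply is that the key premise is not in the available pages. Nothing there says that a held infusion moves day 1 of the next cycle; it might simply be missed. Fulvestrant is scheduled by study day, exemestane is daily, and the grid prints study weeks, all of which lean towards a calendar reading. The available pages are the synopsis and Appendix A. Cycle definitions, delay handling and visit windows may stand in body sections such as Section 7.1.1, to which footnote j refers. This stands, and it makes the point conditional. It does not settle which clock governs: footnote i names the cycle day, and nothing in the available pages makes the week row take precedence.

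A reader might infer more than the text supports:

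- **That any dosing delay moves every scan.** Only delays before the cycle 3 scan carry forward.
- **That bone scans drift in the same way.** Footnote j gives them an 11 to 12 week interval with no cycle anchor; only the grid column ties them to cycle 4.
- **That delay always flatters the delayed arm.** On average it does so for the hazard ratio in the scenarios run, but a 1- or 2-week delay lowers the 6-month proportion.

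It is also fair to say that a shift of 0.01 to 0.03 is minor in an estimation study of 150 subjects, and that half of Arm A delayed with no delay in Arm B is an extreme case.

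**Conclusion.** Appendix A runs two clocks for CT/MRI and, in the available pages, does not reconcile them with each other or with the randomization clock of the 6-month landmark. If early holds move cycle 3 day 1, and if they are commoner in Arm A, the hazard ratio is biased slightly towards AMG 479. For a 2-week delay in Arm A only, a true value of 1 becomes about 0.98, 0.97 and 0.95 with 20%, 30% and 50% delayed; a true 0.727 becomes about 0.71, 0.71 and 0.69. With 20% delayed by 4 weeks, a true 1 becomes about 0.99.

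Both conditions are assumptions. There is no bias if delays are equal between arms or if cycles do not shift. The documents do not support a claim that the trial's estimate is biased, or that the effect would be material beside its 80% interval. The change is still worth making, because it removes an avoidable source of bias from the sole primary endpoint.

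**What to change.** Reword footnote i so that CT/MRI is due at planned times from randomization: 8 weeks, then every 8 weeks (16, 24 and so on), with a window of up to 1 week before each planned date, regardless of dose delays or cycle number. Time each scan from the planned calendar and not from the previous actual scan. The early window keeps the sense of the present 7 to 8 week interval without letting the series drift.

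State that the study-week row governs the imaging rows. Make clear that 8 elapsed weeks corresponds to the grid's study week 9, and that for imaging the count starts at randomization. Reconcile the bone scan's cycle 4 column with footnote j's 11 to 12 week interval on the same calendar. If the body sections already contain such a rule, a cross-reference from footnote i would do.

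The cost is protocol wording. No scans are added, and the sample size and event targets do not change. For subjects with delays, some scans will fall on a day without an infusion visit.
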